# Safety:

S-C1: At least 95% confident that change from Baseline to Day 42 in triglycerides level with the combination treatment ACC+DGAT is less than the ACC monotherapy treatment

Predictive probability of meeting S-C1 at the end of study, based on interim data, will be computed.

## Efficacy:

E-C1: At least 95% confident that the relative reduction from Baseline to Day 42 in whole liver PDFF with the combination treatment ACC+DGAT is larger than the DGAT monotherapy treatment

Predictive probability of meeting E-C1 at the end of study, based on interim data, will be computed.

#### 9. APPENDICES

# 9.1. Categorical Classes for ECG and Vital Signs

# **Categories for QTcF**

Categories for Maximum Post-dose QTc (msec)						
All subjects $\leq 450$ $450 - \leq 480$ $480 - \leq 500$ $>500$						
Categories for Maximum Increase from Baseline in QTc (msec)						
All Subjects	≤30		30 - ≤60		>60	

# **Categories for PR and QRS**

PR (ms)	max. ≥300	
PR (ms) increase	Baseline >200 and	Baseline ≤200 and
from Baseline	max. ≥25% increase	max. ≥50% increase
QRS (ms)	max. ≥140	
QRS (ms) increase	$\geq$ 50% increase	
from Baseline		

# **Categories for Vital Signs**

Systolic BP (mm Hg)	min. <90	
Systolic BP (mm Hg)	max. decrease $\geq 30$	max. increase $\geq 30$
change from Baseline		
Diastolic BP (mm Hg)	min. <50	
Diastolic BP (mm Hg)	max. decrease $\geq 20$	max. increase $\geq 20$
change from Baseline		
Seated pulse rate (bpm)	min. <40	max. >120

• Measurements that fulfill these criteria are to be listed in the report.

#### Calculation of %CBL

%CBL = 100\*(Post-Baseline value – Baseline value) / Baseline value

Page 26
•

#### 9.2. Predictive Probability

#R Code to calculate predictive probability from 'Interim Predictive Probability Calculator'

#Version: 1.01

#Created: 07-Aug-2019

#Inputs:

i\_e\_dir <- 2 # direction of effect of interest

# 1 = Group 1 is greater than Group 2; 2 = Group 1 is less than Group 2

 $i_e_tv \le 0$  # tv = target value

 $i_e_sig <- 0.95 \# confidence level$ 

i\_e\_nAtot <- 28 # sample size for Group 1 at study end

i\_e\_nPtot <- 28 # sample size for Group 2 at study end

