9.1. Sample Size Determination

Approximately 98 subjects will be randomized in a ratio of 1:2:2:2 to four treatment groups A:B:C:D, where A is the placebo group. Assuming an approximate 14% dropout rate this will ensure a minimum of 84 subjects complete the study. This sample size (12 for the placebo group and 24 for the each of monotherapy groups and the combination group) is estimated to provide >90% power to detect a difference of 30% mean reduction in whole liver fat from MRI-PDFF relative to placebo for the PF-05221304 + PF-06865571 combination using a 1-sided Type I error rate of 0.05. This randomization schema will enable detection of a smaller effect requires a larger sample size and hence the sample size is increased for the active arms. With the sample size of 24 completers for each of the PF-05221304 + PF-06865571 combination relative to each monotherapy is approximately 90% using a 1-sided Type I error rate of 0.25. These calculations assume a pooled standard deviation of the log-relative change of 0.32 (based on an internal study).

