# Figure 1. C3711001 Study Design

Determination of eligibility for this study will occur via a sequential, 3 step process, starting at the first screening visit (Screen 1). Subjects identified to be eligible based on Screen 1 AND Screen 2 procedures will proceed to Screen 3 to measure liver fat by MRI-PDFF. For a given subject, this three-step eligibility assessment may take up to 6 weeks.

Once confirmed to be eligible based on results of Screen 3, subjects will progress to a Run in period (Visit 4), at which time subjects will receive single blind placebo for approximately 14 days to ensure compliance with the administration of investigational product (IP). Approximately 4 days prior to randomization, subjects will report to the imaging center (Visit 5) to have a Baseline MRI PDFF scan performed. At Visit 6 (Day 1), subjects will be

randomized to receive 1 of 4 blinded IP regimens (placebo, PF-05221304 monotherapy, PF-06865571 monotherapy, or PF-05221304 plus PF-06865571 combination) for a duration of up to 6 weeks (ie, 42 days). This study includes a total of 11 scheduled outpatient visits to the study site, including 4 visits to the imaging center, and a safety Follow up telephone contact. The total participation, from Visit 1 (Screen 1) to Follow up telephone phone call will be up to approximately 19 weeks.

Approximately 98 subjects (14 for the placebo group, 28 for each of the monotherapy groups and 28 for the combination group) will be randomized at approximately 30 sites (refer to Section 9.1 of the Protocol).

Subjects who are noted to have non evaluable Baseline MRI-PDFF, as determined by the sponsor identified central imaging vendor, should have their MRI-PDFF repeated once; if the images are still non evaluable on single repeat, the subject will be considered as screen failed; otherwise, there are no plans to replace subjects who are prematurely withdrawn.

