## 5.3. Methods to Manage Missing Data

In case of continuous endpoints, all available data will be utilized in the MMRM. The MMRM will provide unbiased estimates in case of missing at random (MAR). For the analysis of safety endpoints, the sponsor data standard rules for imputation will be applied. In case of biomarkers if the concentrations are above the upper limits of quantification such values will be truncated at the upper limit of quantification in all summary tables. If the concentrations are below the lower limits of quantification (LLQ) such values will be imputed by 0.5\*LLQ. However, in listings they will appear as reported.

	Page 15	
CCI		

In all pharmacokinetic data presentations (except listings), concentrations below the limit of quantification (BLQ) will be set to zero. (In listings BLQ values will be reported as "<LLQ", where "LLQ" will be replaced with the value for the LLQ.)

In summary tables and plots of the median values at each time point, statistics will be calculated having set concentrations to missing if one of the following cases is true:

- 1. A concentration has been collected as ND (ie, not done) or NS (ie, no sample),
- 2. A deviation in sampling time is of sufficient concern or a concentration has been flagged anomalous by the pharmacokineticist.

Note that summary statistics will not be presented at a particular time point if more than 50% of the data are missing.

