#### 6. ANALYSES AND SUMMARIES

#### 6.1. Primary Endpoint: Whole Liver PDFF

Primary Analysis

- Analysis endpoint: Whole liver PDFF
- Analysis time points: Day 42
- Analysis population: Full Analysis set
- Analysis methodology: Natural log-transformed individual relative change (RC) from Baseline to Day 42 in whole liver PDFF will be analyzed using the ANCOVA. The model will include natural log-transformed Baseline whole liver PDFF. Baseline diabetes status will be included as a covariate only if at least 1/3 of the subjects have T2DM.

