## 7. INTERIM ANALYSES

If, after randomization of approximately 50% subjects of planned number of subjects, a monthly safety review reveals that the study meets one or more criteria listed in Protocol Section 3.3, an interim analysis will be performed in an un-blinded manner by a prespecified IRC, independent from study team.

Before any interim analysis is initiated, the details of the objectives, decision criteria, dissemination plan, and method of maintaining the study blind as per Pfizer's SOPs will be documented and approved in an IRC charter. The analysis details will be documented and approved in an interim analysis SAP or final SAP.

An IA will be conducted after approximately 50% of randomized subjects reach their Week 6 visit (ie, Visit 10 in Schedule of Activities) or drop out of the study before that visit.

The analysis sets for the IA are:

- 1. Safety Analysis Set: All randomized and treated subjects
- 2. Efficacy/PD Analysis Set: All randomized and treated subjects who completed their Week 6 visit (ie, Visit 10 in Schedule of ActivityActivityActivities) or discontinued the study.

For whole liver PDFF, triglycerides (and total cholesterol, HDL-C, direct LDL-C, Total cholesterol/HDL-C ratio, and non HDL-C, AST, ALT, ALP, GGT), the descriptive summarization and inferential statistical analysis (ANCOVA or MMRM) as indicated in Section 6 will be performed using the Efficacy/PD Analysis Set. Standard safety data as described in the IRC Charter will be summarized using the Safety Analysis Set. The figures related to these descriptive and inferential analyses will be using the "Efficacy/PD Analysis Set".

For whole liver PDFF and triglycerides, additional analysis related to predictive probability will be conducted. The Bayesian predictive probability that the following decision critera will be met at the end of the study given the interim data will be calculated using Pfizer internal validated software. The IRC Statistician will utilize the IA outputs (from ANCOVA analysis for whole liver PDFF and MMRM analysis for triglycerides) to compute the predictive probabilities, and will then provide the probability values to the unblinded programmer to be included in the IA table outputs.

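### The interim predictive probability for E-C1 assumes that all 28 randomised subjects per arm will be evaluable, although the protocol plans for 24, and this overstates it modestly for weak to moderate effects

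*SAP*

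**What the plan says.** SAP Section 7 plans an unblinded look: "An IA will be conducted after approximately 50% of randomized subjects reach their Week 6 visit" or have dropped out before it. For liver fat, criterion E-C1 requires at least 95% confidence that the combination reduces whole liver PDFF more than DGAT2 inhibitor monotherapy does. The SAP states: "Predictive probability of meeting E-C1 at the end of study, based on interim data, will be computed". SAP 5.1 says that interim results may feed into internal business decisions, including stopping for futility.

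The code in Appendix 9.2 fixes the end-of-study size at "28 # sample size for Group 1 at study end", with 28 for Group 2 as well. The interim sizes are left blank, to be filled from the interim ANCOVA (liver fat) or MMRM (triglycerides).

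SAP 2.2 gives 28 as the number to be randomised: "28 for each of the monotherapy groups", and likewise for the combination. Protocol 9.1 plans on fewer being available: "Assuming an approximate 14% dropout rate this will ensure a minimum of 84 subjects complete the study". It bases power on "12 for the placebo group and 24 for the each of monotherapy groups and the combination group".

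The final liver-fat analysis is described in SAP 6.1: "Natural log-transformed individual relative change (RC) from Baseline to Day 42 in whole liver PDFF will be analyzed using the ANCOVA". SAP 5.3 addresses missing data by saying "In case of continuous endpoints, all available data will be utilized in the MMRM". It gives no rule for a missing Day 42 PDFF in the ANCOVA.

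**The concern.** A predictive probability asks how likely the final analysis is to succeed given the interim data. The final n in that calculation should be the number of subjects expected to enter the final analysis. For E-C1 that means subjects with a usable Day 42 scan. Being in the Full Analysis Set does not help, because a subject in that set without a Day 42 value has no response in a single-time-point ANCOVA.

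Entering 28 also makes the code expect more scans than there are subjects left. Suppose 14 of 28 in an arm have reached Week 6 or dropped out, and 12 of those are evaluable. The code then counts 28 − 12 = 16 scans still to come, but only 14 subjects remain. Without replacement or recovery of lost scans, that cannot happen.

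Too large a final n shrinks the assumed final standard error and lowers the bar for E-C1. Over weak to moderate effects, where a futility reading matters most, the shift runs one way, upward.

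**Working it through.** **Design figures.** Protocol 9.1 gives SD 0.32 on the log scale, one-sided 0.05, a 30% reduction, and 24 versus 12 completers. The standard error is 0.32 × √(1/24 + 1/12) = 0.113. Power = Φ(0.357/0.113 − 1.645) = 93%, which agrees with the protocol's claim of more than 90%. Completers: 98 × 0.86 = 84.3 and 28 × 0.86 = 24.1. So the protocol's figures fit together, and 24 is the planned evaluable size of an active arm.

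**SAP formula, equal arms.** Let s be the SD, m the interim n per arm, N the final n per arm, and U = N − m.

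- Final SE = s√(2/N)
- Predictive SD = s√[2(U/N)²(1/m + 1/U)]
- Predictive probability = Φ{[−1.645 × final SE − ln(1 − r)] / predictive SD}, where r is the observed further reduction, combination versus DGAT2 inhibitor monotherapy.

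**Bar for E-C1.** With N = 28 the final SE is 0.0855 and the reduction needed is 1 − exp(−1.645 × 0.0855) = 13.1%. With N = 24 these are 0.0924 and 14.1%. With N = 26 the reduction needed is 13.6%.

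**Worked case.** r = 10%, so −ln(0.90) = 0.1054; m = 12.

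- N = 28: predictive SD 0.0988; (−0.1407 + 0.1054)/0.0988 = −0.357; probability 0.360.
- N = 24: predictive SD 0.0924; (−0.1520 + 0.1054)/0.0924 = −0.504; probability 0.307.
- Excess: 5.3 points.

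**Range.** SD 0.32. The interim and final counts are assumptions, because the SAP leaves interim n blank. Each cell shows the probability with 28 entered, then with the lower N, and the excess in points.

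| Interim n; lower N | r = 0% | r = 5% | r = 10% | r = 16.5% |
|---|---|---|---|---|
| 12; 24 | 0.077, 0.050 (2.7) | 0.183, 0.138 (4.5) | 0.360, 0.307 (5.3) | 0.656, 0.621 (3.5) |
| 12; 26 | 0.077, 0.064 (1.3) | 0.183, 0.162 (2.1) | 0.360, 0.336 (2.4) | 0.656, 0.640 (1.6) |
| 13; 25 | 0.063, 0.043 (1.9) | 0.165, 0.131 (3.4) | 0.350, 0.308 (4.2) | 0.667, 0.641 (2.6) |
| 14; 26 | 0.050, 0.038 (1.2) | 0.148, 0.125 (2.3) | 0.340, 0.311 (2.9) | 0.679, 0.662 (1.7) |

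The 16.5% is also an assumption. The effect size for combination versus monotherapy is not legible in Protocol 9.1, so it was solved from the stated 90% power at one-sided 0.25 with 24 per arm: (0.674 + 1.282) × 0.32 × √(2/24) = 0.181 log units, which is 16.5%.

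**Where it stops.** For 12 and 24, the excess is 1.9 points at r = 20%, 0.3 at 25% and zero at 27.0%. Beyond that it is at most 0.1 point the other way. It reaches zero at 27.5% for 12 and 26, and at 24.1% for 14 and 26.

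**Other settings.** With interim n from 10 to 14, the peak excess is 4.4 to 6.4 points against 24 and 2.0 to 2.9 against 26. For 12 and 24, with SD 0.25 or 0.40 the peak stays at 5.3 points, and the excess reaches zero at 21.8% and 32.6% respectively.

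**The case against.** The strongest reply is that 28 is a ceiling and 24 a floor, so using 28 is a convention that needs a label rather than an error. The protocol words its completer total as a minimum. Several provisions could raise the evaluable number: subjects who stop treatment stay in follow-up, and withdrawn subjects may be replaced (both Protocol 6.5, although Protocol 3.1 and SAP 2.2 plan no replacement), and some early-termination scans are taken (Schedule of Activities, footnote h). Dropout actually seen by the time of the interim is not in the documents. This stands as a reason to report a range, which is why 26 is shown beside 24; with 27 the excess would be only about 1 point. It does not justify 28 as the only input, which requires no loss at all.

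The shift is also small beside other uncertainty. At 12 per arm the interim SE of the difference is 0.32 × √(2/12) = 0.131 log units. One SE either side of an observed 10% moves the 28-per-arm value from 0.05 to 0.83. The code treats the interim SD as known, and moving it from 0.32 to 0.36 changes the 10% result from 0.360 to 0.317. All of this is true. But that is sampling noise that cannot be avoided, whereas this is a systematic choice of input that departs from the protocol's own assumption and can be removed.

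Finally, no probability cut-off appears in either document (decision criteria are left to the IRC charter), and the IRC also sees the adjusted means, their difference and standard errors. So no wrong decision can be demonstrated. That limits the weight of the point without removing it.

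**Conclusion.** The point holds and should be corrected, at modest weight. For E-C1, 28 is the randomised count used where the evaluable count belongs. At SD 0.32 and 12 evaluable per arm at the interim, this overstates the predictive probability by 2.7 to 5.3 points for observed further reductions of 0 to 16.5% if 24 finish evaluable, and by 1.3 to 2.4 points if 26 do. If all 14 were evaluable at the interim and only 24 at the end, the peak would be 6.4 points. The excess is negligible from about 25% upward.

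This rests on the assumed interim counts and on the absence of any stated imputation for the Day 42 ANCOVA. It concerns E-C1 only. The triglyceride criterion S-C1 uses the same inputs, but its MMRM draws on partial data from subjects who drop out, so these figures do not carry over. The final analysis and its error rates are untouched.

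**What to change.** In SAP Appendix 9.2, for liver fat:

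1. Set `i_e_nAtot` and `i_e_nPtot` to the number expected to have a Day 42 PDFF. Use either the protocol's 24, or the interim evaluable count plus 0.86 times all remaining planned subjects in that arm. Remaining means 28 minus those who have reached Week 6 or dropped out, so it includes subjects not yet randomised. With 12 of 14 evaluable this gives 12 + 0.86 × 14 = 24.0; with all 14 evaluable, 14 + 0.86 × 14 = 26.0. Counting only those already on study would be wrong: with 8 on study and 6 still to be randomised it would give 12 + 0.86 × 8 = 18.9, and a probability of 0.201 instead of 0.308 at an observed 10%.
2. State that the interim n is the number of subjects contributing to the interim ANCOVA.
3. Report the result with 28 beside it, labelled as the no-dropout case.

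The cost is two input lines kept separate from those for triglycerides, one sentence, and one output column. The headline probability becomes slightly less favourable. If more than 24 finish evaluable, using 24 understates it by up to the same margin, and the 0.86 rule is slightly conservative for subjects already part-way through treatment. Keeping the 28 column lets the IRC see both ends.

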# The following inputs will be taken from the ANCOVA (liver fat) or MMRM (trigylcerides) interim analysis

i\_r\_nAint <- # sample size for Group 1 at interim

i\_r\_nPint <- # sample size for Group 2 at interim

i\_r\_meanA <- # model-adjusted mean for Group 1 at interim from MMRM or ANCOVA

i\_r\_meanP <- # model-adjusted mean for Group 2 at interim from MMRM or ANCOVA

i\_r\_sigma <- # ssigma estimated at interim from MMRM or ANCOVA

# Adapted from equations 1-4 from 'Bayesian Interim Predictive Analysis Guidance' document (v1.0 19 September 2018)

# Derived:

i\_nAU <- i\_e\_nAtot-i\_r\_nAint

```
i nPU <- i e nPtot-i r nPint
 if(i e dir==1){ #Greater than
  z \leq qnorm(i e sig)
 } else if(i_e_dir==2){ #Less than
  z \leq qnorm(1-i e sig)
 }
 #Calculate numerator of equation:
 postSD <- i r sigma*sqrt((i e nAtot+i e nPtot)/(i e nAtot*i e nPtot))</pre>
 num_eq <- i_e_tv + z*postSD - (i_r_meanA - i_r_meanP)
 #Calculate denominator of equation:
 den eq <-
i r sigma*sqrt(((i nAU/i e nAtot)^2)*(1/i r nAint+1/i nAU)+((i nPU/i e nPtot)^2)*(1/i
r nPint+1/i nPU))
 #Determine predictive probability:
 eq result <- num eq/den eq
 if(i e dir==1){ #Greater than
  predProb <- 1-pnorm(eq result)</pre>
 } else if(i e dir==2){ #Less than
  predProb <- pnorm(eq result)</pre>
 }
```

#Predictive probability:

print(paste0(100\*predProb,"%"))

# **Example Output: Summary of Predictive Probability for IA**

# Safety:

Treatment	LSM (S.E.)	Difference vs. PF-05221304 (S.E)	Predictive Probability of Passing S-C1*
PF-06865571 + PF-05221304 (ie, DGAT + ACC)	xx.xx (xx.xx)	xx.xx (xx.xx)	0.xx
PF-05221304 (ie, ACC)	xx.xx (xx.xx)		

\*S-C1 is the safety criterion defined in Section 7

S.E = Standard Error

# Efficacy:

Treatment	LSMeanLSMeanLSM (S.E.)	Difference vs. PF- 06865571 (S.E)	Predictive Probability of Passing S-C1*
PF-06865571 + PF- 05221304 (ie, DGAT + ACC)	xx.xx (xx.xx)	xx.xx (xx.xx)	0.xx
PF-06865571 (ie, DGAT)	XX.XX (XX.XX)		

\*E-C1 is the efficacy criterion defined in Section 7

S.E = Standard Error
